2. SIGN CONSENT
3. ETDRS- eyes check (screening)
4. MONOFILAMENT TEST- put the shoes on (screening)
5. Vestibular examination: (screening)- Dizziness Handicap Inventory (DHI) questionnaire (in REDCAP)
6. Auditory screening for the control group (screening older controls for ARHL rather than a full audiogram to everyone).

---

Exclusion due to one of the followings:

- ETDRS - visual impairment above 20/63
- MONOFILAMENT - No protective sensation at the bottom of their feet.
- DHI- Participants will be included with a score of 10 or below indicating no more than minimal dizziness.
- Auditory screening – participants in the control group that will exhibit a PTA higher than 40 dB (0.5–4 kHz) in the better ear (moderate HL and above) will be excluded.

---

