13. TMT A & B
14. Practice trial: Walking back and forth the corridor

15. Randomized Trial- each trial will be done 1 time (without hearing aid):

1. Single cognitive task sub1 - [Baseline] while sitting (serial subtraction of 1) + record with phone
2. Single cognitive task sub3 - [Baseline] while sitting (serial subtraction of 3) + record with phone
3. Single motor – [Baseline] Walking on the ground for 1 min a 10 m long corridor – recording with a stopwatch
4. Dual task cognitive sub1 (DT\_sub1) - serial subtraction of 1 + #3 - recorded with stopwatch + record with phone
5. Dual task cognitive sub3 (DT\_sub3) - serial subtraction of 3 + #3 - recorded with stopwatch + record with phone

Using REDCAP:

16. DEMOGRAPHIC questionnaire (descriptive)
17. ABC – In healthy young adults ask: “have you never had any concern regarding: balance?” – if yes- fill up the questionnaire. (descriptive)

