### **Data analysis:**

Each variable was inspected for extreme outliers (i.e., data points that fell more than 4 standard deviations [SD] away from the mean) using summary statistics and box plots. An extreme outlier was excluded from the final analysis. Normality of the variables was determined based on skewness and kurtosis. Number that is greater than +1 or lower than -1 indicate a substantially skewed distribution. For kurtosis, if the number is greater than +1, the distribution is too peaked and less than -1 indicates a distribution that is too flat. If the distribution was found to deviate from normality, non-parametric statistical analysis was conducted.

Descriptive statistics described the study sample for age, sex, height, weight, race, current medication, education level, exercise level, DHI, ABC, history of falls, MoCA and HI- MoCA. To determine if the groups are similar with respect to background measures and demographics a comparison of the three groups Normal hearing, Mild BHL and > Moderate BHL (moderate, moderately-severe, severe and profound) was done using one-way analysis of variance (ANOVA) or non-parametric Kruskal-Wallis Test for continuous measures and Chi-square analyses for categorical measures (e.g., gender).

For Aim #1: Compare single task (=ST) gait parameters between individuals age and education-matched with Mild BHL, > Moderate BHL and controls with Normal hearing and Aim #3: Compare the effect of a cognitive task on gait parameters (=DT) between age and education-matched people with Mild BHL, > Moderate BHL and control with Normal hearing: For the primary outcome measure, gait speed and its variability, and secondary outcome measures (stride length, stride time and their variability) during the 1-min walk, a mixed model repeated measures (RM)- ANOVA was conducted with 1 within-factor (task) of 2 levels (ST and DT ['subtraction 3']) and 1 between factor (group) of 3 levels (Normal hearing, Mild BHL, Moderate BHL). When the distributions were found to deviate from normality the Kruskal-Wallis' test was conducted for a between-group comparison and the Wilcoxon signed-rank test for a within-group comparison. Since I had a significant difference with age, I adjusted for age the ANOVA comparison.

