Partial Eta Square (PET) Effect Size was reported for each main effect and interaction (small effect, PET  $\geq 0.08$ ; middle effect, PET  $\geq 0.20$ ; and high effect, PET  $\geq 0.32$ ). P-values with a value of  $p < 0.05$  were considered statistically significant. Bonferroni corrections were applied to post hoc comparisons as applicable.

For Aim #2: Compare cognitive function (i.e., the Neurocognitive Index) between individuals age and education-matched with Mild BHL, > Moderate BHL and controls with Normal hearing. One way ANOVA (or non-parametric Kruskal-Wallis Test) was used to compare the Neurocognitive Index between the three groups. Moreover, one way ANOVA (or non-parametric Kruskal-Wallis Test) was used to compare the secondary outcome measures, i.e., Composite Memory, Verbal Memory, Visual Memory, EF, Cognitive Flexibility, Complex RT, Working Memory and Sustained Attention and the cognitive ST and DT performance. I used one-way ANOVA with the dependent variable, the cognitive domain (Neurocognitive Index or any of the secondary outcome measures), and group as independent variable. For the raw scores I used the ACNOVA to adjust for age since we had significant age difference and these results do not present an age-matched score. Cohen's d effect size was calculated per comparison and was defined 'small' effect size as  $d = 0.2$ , 'medium' effect size as  $d = 0.5$  and a 'large' effect size as  $d = 0.8$ .

For Aim #4: Explore whether cognitive performance (i.e., the Neurocognitive Index) is correlated with DTC per group. One way ANOVA (or non-parametric Kruskal-Wallis Test) was used to compare the DTC between the three groups. Correlations between the cognitive domains and DTC were assessed using Pearson's correlation (or its non-parametric equivalent Spearman's, if the distributions are found to deviate from normality) for continuous variables. Pearson's correlation for each comparison was defined as 'little to none' for  $r = 0-0.24$ , 'fair' for  $r = 0.25-0.49$ , 'moderate to good' for  $r = 0.50-0.74$  and 'good to excellent' for  $r = 0.75-1.00$ . SPSS version 27 IBM (NY, US) was used for all statistical analysis.

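### Aim 4 compares dual-task cost (DTC) between the three hearing groups without age adjustment, although the plan reports a significant age difference and adjusts for it in Aims 1 to 3

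*Combined protocol and SAP*

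**What the plan says.** All points below are in the Data analysis section unless another place is named.

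- **Design intent.** Aim 1 sets out to compare "gait parameters between individuals age and education-matched with Mild BHL" and the other two groups; Aims 2 and 3 also describe the groups as matched on age and education.
- **What happened.** The Aim 1/3 paragraph ends: "Since I had a significant difference with age, I adjusted for age the ANOVA comparison".
- **Aim 2.** The adjustment is stated again, limited to raw scores and with its reason: "we had significant age difference and these results do not present an age-matched score".
- **Aim 4, objective.** "Explore whether cognitive performance (i.e., the Neurocognitive Index) is correlated with DTC per group".
- **Aim 4, group comparison.** "One way ANOVA (or non-parametric Kruskal-Wallis Test) was used to compare the DTC between the three groups". No covariate is named and no reason is given for leaving age out. DTC is not defined and is not described as age-normed.
- **Aim 4, correlations.** Pearson or Spearman, with no partial correlation for age.

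The procedures suggest that the age range may be wide. Screening step 6 refers to "screening older controls for ARHL rather than a full audiogram to everyone", and the ABC item (step 17) carries an instruction beginning "In healthy young adults ask". Neither shows how ages were distributed over the three analysis groups.

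**The concern.** The plan names a confounder, handles it in three aims and omits it in the fourth, on the same three groups. By its own Aim 2 reasoning, a measure that is not age-matched needs adjustment when the groups differ in age, and DTC appears to be such a measure. Being a within-person contrast does not protect DTC: age cancels only if the cost of the second task does not itself change with age, and the plan does not claim that.

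Two things are at stake. First, a group difference in DTC that is due to age could be read as due to hearing loss. Second, if gait DTC is the dual-task minus single-task difference, the Aim 4 ANOVA is the unadjusted form of the age-adjusted group-by-task interaction in Aim 3. The report could then give a significant group difference in one place and a non-significant one in the other, from the same data.

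**Working it through.** **Is age adjustment supplied anywhere for Aim 4?** The only candidate is the sentence that closes the Aim 1/3 paragraph. It refers to one ANOVA comparison. Aim 2 then states its own adjustment and restricts it to raw scores, which a general rule would have made unnecessary. The natural reading is that Aim 4 is unadjusted.

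**Inputs.** From the plan: three groups, significance at p < 0.05, one-way ANOVA or Kruskal-Wallis. Assumed, because the documents do not give them: n per group (15 to 30), age gap D between the extreme groups in within-group SDs (0.8 to 1.2), and within-group age-DTC correlation r (0.2 to 0.4). No group effect exists once age is accounted for. The plan states no figure that could be reproduced.

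**False-positive rate of the unadjusted ANOVA.** With within-group SDs of 1, the DTC group means differ by r times the differences in mean age. The F statistic is noncentral with 2 and 3n − 3 degrees of freedom and

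λ = n × Σ[r × (group mean age − grand mean age)]².

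If the middle group lies halfway, the age deviations are −D/2, 0 and D/2, so λ = n r² D² / 2. If the two younger groups have equal mean age, λ = 2 n r² D² / 3.

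| n per group | Age pattern | D = 0.8, r = 0.2 | D = 1.2, r = 0.4 |
|---|---|---|---|
| 15 | halfway | λ = 0.192, 6.4% | λ = 1.728, 18.9% |
| 20 | halfway | λ = 20 × 0.04 × 0.64 / 2 = 0.256, 6.9% | λ = 20 × 0.16 × 1.44 / 2 = 2.304, 24.3% |
| 30 | halfway | λ = 0.384, 7.9% | λ = 3.456, 35.4% |
| 20 | two younger equal | λ = 0.341, 7.5% | λ = 3.072, 31.3% |

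With r = 0.1, n = 20 and the middle group halfway, the rate is 5.5% to 6.0%. With r = 0 it stays at 5%.

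Simulation over the halfway cells gives 6% to 35% for ANOVA, 6% to 33% for Kruskal-Wallis and 4.7% to 5.6% for ANCOVA. The ANCOVA result assumes a linear age effect common to all groups.

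**Tied to the plan's own threshold.** Instead of assuming an age gap, fix the observed age F statistic at the value for a given p-value and simulate DTC. The ranges cover n = 15 to 30.

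| Age difference at | r = 0.2 | r = 0.4 |
|---|---|---|
| p = 0.05 | 6.0–6.3% | about 10% |
| p = 0.001 | 9.0–9.4% | 22.3–23.7% |

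Group size hardly matters here, because the p-value already fixes the age imbalance relative to its sampling error.

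**Conflicting answers.** At n = 20, middle group halfway, the unadjusted test is significant and the age-adjusted test is not in 3.3% (D = 0.8, r = 0.2) to 21.2% (D = 1.2, r = 0.4) of simulated trials. With r = 0 this still happens in 1.0% to 1.4%, so the low end is only about 2 percentage points above that background.

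**Correlations.** These are run within each group, so the between-group age gap does not confound them. Age spread within a group can still induce a correlation with a raw cognitive score, of about (age-DTC r) × (age-cognition r). With an assumed age-cognition correlation of 0.3 to 0.5, this is 0.2 × 0.3 = 0.06 to 0.4 × 0.5 = 0.20. That lies inside the plan's lowest band (0 to 0.24), so this part is minor.

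**The case against.** - **Aim 4 is exploratory and its objective is the per-group correlation.** This stands. The primary outcome, gait speed and its variability, has an age-adjusted ANOVA, and only the accompanying DTC comparison is affected. That limits the weight of the point; it does not make the comparison unconfounded.
- **The age sentence may be meant for every ANOVA, and an adjustment may have been made but not reported.** This cannot be excluded, but its position and Aim 2's separate, narrower statement count against it. Even on that reading, the Kruskal-Wallis alternative takes no covariate, so the adjustment would be lost whenever DTC is non-normal.
- **The same Kruskal-Wallis gap exists in Aims 1/3 and Aim 2.** Correct, and it reaches the primary outcome. The contrast with the other aims is therefore sharpest on the parametric branch. This widens the problem and does not excuse Aim 4.
- **The size is unknown, and the upper figures need a large age gap together with r = 0.4.** This stands. Nothing in the documents supports a particular r, and a barely significant age difference gives only about 6% to 10%.
- **The conflict with Aim 3 depends on how DTC is defined.** This also stands. If DTC is a percentage of single-task performance or a cognitive cost, the two tests are not the same contrast.
- **The instruction about healthy young adults belongs to a questionnaire.** True. It does not show that young adults were in the three analysed groups, and the conclusion does not rest on it.

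**Conclusion.** The concern holds. As written, Aim 4 compares DTC across groups that the plan itself found to differ in age, with no adjustment and no reason given, contrary to the rule it applies in Aim 2. Under the assumptions shown, the false-positive rate runs from barely above 5% (weak age-DTC correlation) through 6% to 10% (age difference just significant) to 24% at 20 per group, or 35% at 30 per group, with a large age gap and r = 0.4. The documents do not show where this study falls in that range.

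The change should be made, but the point is not critical, because the comparison is part of an exploratory aim. Confidence is moderate: the reading of the text is firm, while the size depends entirely on assumed inputs. The correlation point is minor and concerns raw cognitive scores only.

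**What to change.** 1. Define DTC: give the formula, and say whether it is gait cost, cognitive cost or both.
2. Compare DTC between groups by ANCOVA with age as covariate, after checking that the age relation is linear and that its slope is similar across groups. If residuals are non-normal, use a rank-based ANCOVA instead of Kruskal-Wallis. The same replacement would close the gap in the non-parametric branches of Aims 1/3 and of the Aim 2 raw scores.
3. If an age adjustment was already made for Aim 4, say so.
4. Where the correlated cognitive score is raw, report the within-group correlation with DTC as an age-partial Pearson or Spearman correlation. Age-matched scores need no change.

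The cost is one degree of freedom per test, and two more for the slope check. Age is already recorded, and the plan already uses ANCOVA in Aim 2, so no new data or methods are needed apart from the rank-based fallback.

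### The group difference in dual-task effect is apparently tested twice, as the age-adjusted Aim 3 interaction and as an Aim 4 ANOVA on an undefined DTC with no stated age adjustment

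*Combined protocol and SAP*

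**What the plan says.** All the relevant text is in the Data analysis section.

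- **Aim 3** is to "Compare the effect of a cognitive task on gait parameters (=DT) between age and education-matched people" in the three hearing groups. The model is a mixed repeated-measures ANOVA with "1 within-factor (task) of 2 levels (ST and DT ['subtraction 3']) and 1 between factor (group) of 3 levels". Partial eta squared "was reported for each main effect and interaction".
- **Age** is handled in the Aims 1 and 3 paragraph: "Since I had a significant difference with age, I adjusted for age the ANOVA comparison".
- **Non-normal data** in Aims 1 and 3 go to Kruskal-Wallis between groups and Wilcoxon signed-rank within groups.
- **Aim 4** is worded as a correlation aim: "Explore whether cognitive performance (i.e., the Neurocognitive Index) is correlated with DTC per group". Its first analysis is nevertheless a group comparison: "One way ANOVA (or non-parametric Kruskal-Wallis Test) was used to compare the DTC between the three groups". The correlations follow: "Correlations between the cognitive domains and DTC were assessed using Pearson's correlation", or the Spearman equivalent.

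DTC is never expanded. There is no formula, no named gait or cognitive outcome, and no named dual-task condition. The Aim 4 paragraph states no age adjustment. Bonferroni correction is stated for post hoc comparisons only.

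**The concern.** With only two task levels, the group-by-task interaction is a comparison of the groups on dual-task minus single-task performance. That is also what a group comparison of dual-task cost does. The plan therefore appears to test one question in two places, with different covariate handling and possibly on different scales, and does not say which result answers it.

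Two things are at stake. First, the groups differ significantly in age by the plan's own account, so an age-adjusted and an unadjusted test can give different answers. Second, if DTC is a percentage, a group difference in relative cost can arise from a difference in walking speed alone, with the absolute cost identical in every group. A reader could then take a restatement of the Aim 1 comparison for evidence that hearing loss changes dual-task cost.

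**Working it through.** The documents give no sample size, mean, SD or power figure, so there is no stated number to reproduce. All speeds, costs, SDs and group sizes below are assumptions.

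**Step 1. DTC as a difference.** Let d = ST − DT for each person (the sign does not affect F). With two task levels, the interaction sum of squares is half the between-group sum of squares of d, and its error term is half the within-group sum of squares of d. The halves cancel, so F(group × task) = F(one-way ANOVA on d), with 2 and N − 3 degrees of freedom. A simulated data set of 60 people gave F = 0.2906 both ways. On this definition the unadjusted Aim 4 test is the Aim 3 interaction with the age covariate left out.

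**Step 2. DTC as a percentage.** Write S for a group's mean single-task speed and C for its mean cost. Equal absolute cost means C is the same in all groups. Equal relative cost means C/S is the same in all groups. At the level of group means, both hold only if S is equal across groups or C = 0.

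| Assumed speeds (m/s) | Equal cost of 0.14 m/s, as % of ST | Equal cost of 12%, in m/s |
|---|---|---|
| Wide gap: 1.30 / 1.20 / 1.05 | 10.8 / 11.7 / 13.3 | 0.156 / 0.144 / 0.126 |
| Modest gap: 1.25 / 1.20 / 1.15 | 11.2 / 11.7 / 12.2 | 0.150 / 0.144 / 0.138 |

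Each entry is 0.14/S or 0.12 × S.

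**Step 3. How often the tests are positive.** Simulation used 20,000 data sets per scenario, between-person SD 0.18 m/s, cost SD 0.07 m/s, alpha 0.05, n = 20 or 30 per group, and no age adjustment. The off-scale test is the one whose null is false: percentage DTC when absolute cost is equal, and the interaction when relative cost is equal.

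| Scenario | Off-scale test positive | Either test positive |
|---|---|---|
| Wide gap, n = 20 | 19-20% | 21-22% |
| Wide gap, n = 30 | 27-28% | 29-30% |
| Modest gap, n = 20 to 30 | 7-8% | about 9-10% |
| Equal speeds | about 5% | about 7% |
| Speeds differ, mean cost zero | about 5% | about 6% |

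The size of the speed gap drives the result. In SD units the outer groups differ by (1.30 − 1.05)/0.18 = 1.39 in the wide case and (1.25 − 1.15)/0.18 = 0.56 in the modest one. The plan itself labels d = 0.8 as large (in Aim 2, for the cognitive comparisons).

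A second set of assumptions (SD 0.15 m/s, cost 0.12 m/s or 10%, cost SD 0.08 m/s, n = 20, 3,000 runs) gave the same pattern. The off-scale test was positive in 9-11% with speeds 1.25/1.15/1.05 and in 26-31% with 1.3/1.1/0.9.

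**Step 4. The non-parametric route.** Kruskal-Wallis between groups and Wilcoxon within groups, as described for Aims 1 and 3, do not test group × task. On that route the DTC comparison in Aim 4 is the only stated test of whether the dual-task effect differs by group.

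**The case against.** **The two nulls can both be true.** A reader might infer that, once groups differ in single-task speed, the two tests cannot both have a true null. The documents do not support that. It requires DTC to be a percentage, which is not stated, and a non-zero mean cost. If DTC is the plain difference, the two nulls are identical. Even for a percentage averaged over individuals there are exceptions. Take two groups with speeds {0.9, 1.3} and {1.1, 1.5} m/s and costs {0.045, 0.195} and {0.165, 0.075} m/s. Their mean speeds are 1.1 and 1.3, yet both have mean cost 0.12 m/s and mean percentage cost 10%. This objection stands, and the point is worded to respect it.

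**A speed difference is not predicted.** Aim 1 compares single-task gait. It states no expected difference or direction. This stands too.

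**The percentages are not false-positive rates.** When relative cost is equal and speeds differ, absolute cost really does differ, so most of the 21-30% is power on the other scale. The inflation from testing twice is only the rise from 5% to about 7% at equal speeds; two independent tests would give 1 − 0.95² = 9.75%. This stands. The problem is an ambiguous claim more than an inflated error rate.

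**DTC may not be gait cost.** The protocol also records cognitive performance in single and dual task, walking with subtraction of 1, and a dual-task TUG. DTC on any of these would not duplicate the gait interaction. The gait reading is natural, because Aim 3 is where the task effect is analysed, but it is an inference.

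**A hierarchy partly exists.** The primary outcome is tied to the repeated-measures ANOVA, and Aim 4 is worded as exploratory. That helps, but it neither defines DTC nor explains why a group test sits under a correlation aim without the age adjustment.

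**Conclusion.** The concern holds in a conditional form. If DTC is a gait measure, the group difference in dual-task effect is tested twice: once with age adjustment (Aim 3) and once with none stated (Aim 4), in groups reported to differ in age. If DTC is a difference, the second test is the first without the covariate. If it is a percentage, the second test has another null and will generally disagree with Aim 3 when mean cost is non-zero and single-task speeds differ.

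The size is illustrative. On the assumed inputs, without age adjustment and with n = 20 to 30 per group, at least one test is positive in about 9-10% of trials with a modest speed gap and 21-30% with a wide one. The difference in age adjustment is plain in the text and needs none of these assumptions. The change should be made because it is cheap and settles which result supports a claim about hearing loss and dual-task cost.

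**What to change.** 1. Define DTC: the outcome, the dual-task condition and the formula.
2. Make the age-adjusted group × task term the only inferential test of the Aim 3 question. If relative cost is the intended claim, fit the model to log gait speed. The interaction then compares log(DT/ST), which corresponds to a percentage DTC because DT/ST = 1 − (ST − DT)/ST.
3. In Aim 4, show DTC by group as means with confidence intervals and keep the correlations as they are.
4. Do not delete the between-group DTC test outright. Keep it for the non-parametric route, where no interaction test exists, and adjust it for age, for example by a rank-based ANCOVA.
5. If the absolute and relative scales disagree, state that the conclusion depends on the scale.

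The cost is a few lines of SAP wording and a rerun of one model. One largely redundant significance test is lost when the parametric model is used.
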